	Sensitivity 1	Change from parent-study baseline in WOMAC Stiffness at Visit 2E (Week 24)	FAS	Prohibited medications and NSAID/acetaminophen use: treatment policy strategy; analysis will be conducted regardless of use of prohibited medications or NSAID/acetaminophen use.	Difference in the change from parent-study baseline between LOR and placebo using parent-study baseline-adjusted ANCOVA with missing data imputed using the MI method.
	Sensitivity 2	Change from parent-study baseline in WOMAC Stiffness at Visit 2E (Week 24)	mFAS	Prohibited medications and NSAID/acetaminophen use: treatment policy strategy; analysis will be conducted regardless of use of prohibited medications or NSAID/acetaminophen use.	Difference in the change from parent-study baseline between LOR and placebo using parent-study baseline-adjusted ANCOVA with available data.
	Sensitivity 3	Change from parent-study baseline in WOMAC Stiffness at Visit 2E (Week 24)	PPAS	1) Prohibited medications: principal stratum strategy; subjects who used prohibited medications will be excluded from this analysis. 2) NSAID/acetaminophen: treatment policy strategy; analysis will be conducted regardless of NSAID/acetaminophen use.	Difference in the change from parent-study baseline between LOR and placebo using parent-study baseline-adjusted ANCOVA.
Estimand is repeated using the OA-07-study baseline					

Other	Estimator	Variable	Population	Other intercurrent events	Population level summary
	Main	Change from parent-study baseline in mJSW at Visit 6E (Week 100)	FAS: “Placebo-LOR” subjects	Prohibited medications and NSAID/acetaminophen use: treatment policy strategy; analysis will be conducted regardless of use of prohibited medications or NSAID/acetaminophen use.	Difference in the change from parent-study baseline between “Placebo-LOR” subjects compared to test values (carry forward and progression assumptions) derived from the Placebo group change from baseline estimates at Visit 3E (Week 48). Estimates will use parent-study baseline-adjusted ANCOVA with available data.
	Main	Change from parent-study baseline in mJSW at Visit 6E (Week 100)	FAS: “LOR-LOR” subjects	Prohibited medications and NSAID/acetaminophen use: treatment policy strategy; analysis will be conducted regardless of use of prohibited medications or NSAID/acetaminophen use.	Difference in the change from parent-study baseline between “LOR-LOR” subjects compared to test values (carry forward and progression assumptions) derived from the Placebo group change from baseline estimates at Visit 3E (Week 48). Estimates will use parent-study baseline-adjusted ANCOVA with available data.
	Main	Change from parent-study baseline in mJSW at Visit 6E (Week 100)	FAS: Pooled “Placebo-LOR” and “LOR-LOR” subjects	Prohibited medications and NSAID/acetaminophen use: treatment policy strategy; analysis will be conducted regardless of use of prohibited medications or NSAID/acetaminophen use.	Difference in the change from parent-study baseline between pooled “Placebo-LOR” and “LOR-LOR” subjects compared to test values (carry forward and progression assumptions) derived from the Placebo group change from baseline estimates at Visit 3E (Week 48). Estimates will use parent-study baseline-adjusted ANCOVA with available data.
Estimand is repeated using the OA-07-study baseline					

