4.5.3 Prohibited Medications, Treatments, and Procedures

During the conduct of the study, certain medications, treatments, and procedures were prohibited (see Protocol Section 7.6). The overall intent of these prohibitions was to minimize any possible bias in the assessment of the clinical trial endpoints. However, the protocol did allow for the use of these prohibited therapies if, and only if, they were required to ensure subject safety. Investigators were instructed to notify the sponsor's Medical Monitor, who would note the prohibited therapy as a protocol deviation. These deviations were categorized as major or minor depending on the nature and timing of the interventions. Subjects were not automatically discontinued based upon prohibited therapy use, allowing for continued data collection and assessment of the impact of prohibited therapy on key endpoint data.

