6.2 Per-Protocol Analysis Set

The Per-Protocol Analysis Set (PPAS) includes FAS subjects who received the correct treatment, completed Visit 6E (Week 100) and did not have any major protocol deviations in the current or parent study that might impact the evaluation of efficacy outcomes (see [Section 8.2](#)). Subjects will be analyzed as randomized for the PPAS.

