8.2 Protocol Deviations

A protocol deviation is defined as any noncompliance with the clinical trial protocol requirements. The noncompliance may be either on the part of the subject, the Investigator, or the study site staff.

Deviations are summarized into one of the following categories:

- Informed Consent Form
- Enrollment
- Procedures
- Labs/Specimens
- Study Visits
- Investigational Product
- Subject Non-Compliance
- Serious Adverse Events

Deviations are categorized as major or minor by a cross-functional team according to pre-defined criteria established in the Protocol Deviation Classification Guideline.

- A major deviation is defined as a divergence from the protocol that materially (a) reduces the quality or completeness of efficacy data, (b) makes the informed consent inaccurate, or (c) impacts a subject's safety, rights or welfare.
- A minor deviation is defined as a divergence from the protocol that deviates from the procedures and guidelines outlined in the protocol, but is not classified as a major deviation (i.e. the deviation does not materially (a) reduce the quality or completeness of the data, (b) make the informed consent inaccurate, or (c) impact a subject's safety, rights or welfare).

Protocol deviations may result in subject exclusion from the PPAS. All protocol deviations were reviewed by study team members to determine if the deviation could reasonably affect/confound interpretation of key efficacy endpoints and should result in the subject being excluded from the PPAS. 27 subjects (29 protocol deviations) with the following types of deviations were excluded from PPAS:

- Major parent study protocol deviation impacting efficacy outcome(s):

- Major EN01 deviations (subject randomized or enrolled without meeting eligibility criteria): n = 3
- Major NC03 deviations (prohibited procedure done): n = 2
- Major OA-07 study protocol deviation impacting efficacy outcome(s):
 - Major NC03 deviations (prohibited procedure done): n = 1
 - Major NC04 deviations (prohibited concomitant medication taken) that would affect efficacy analysis at Visit 3E (Week 48) or Visit 6E (Week 100): n = 5
 - Major P01 deviations (procedure performed incorrectly): n = 5
 - Major P02 deviations (Procedure not attempted or not performed): n = 13

A final list of protocol deviations resulting in subject or data exclusion from the PPAS can be found in Appendix 1 – Protocol Deviations Leading to Exclusion from Per-Protocol Analysis.

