	Sensitivity 3	Change from parent-study baseline in WOMAC Function at Visit 3E (Week 48)	PPAS	1) Prohibited medications: principal stratum strategy; subjects who used prohibited medications will be excluded from this analysis. 2) NSAID/acetaminophen: treatment policy strategy; analysis will be conducted regardless of NSAID/acetaminophen use.	Difference in the change from parent-study baseline between LOR and placebo using parent-study baseline-adjusted ANCOVA.
Estimand is repeated using the OA-07-study baseline					

Secondary	Estimator	Variable	Population	Other intercurrent events	Population level summary
	Main	Change from parent-study baseline in Pain NRS at Visit 2E (Week 24)	FAS	Prohibited medications and NSAID/acetaminophen use: treatment policy strategy; analysis will be conducted regardless of use of prohibited medications or NSAID/acetaminophen use.	Difference in the change from parent-study baseline between LOR and placebo using parent-study baseline-adjusted ANCOVA with available data.
	Sensitivity 1	Change from parent-study baseline in Pain NRS at Visit 2E (Week 24)	FAS	Prohibited medications and NSAID/acetaminophen use: treatment policy strategy; analysis will be conducted regardless of use of prohibited medications or NSAID/acetaminophen use.	Difference in the change from parent-study baseline between LOR and placebo using parent-study baseline-adjusted ANCOVA with missing data imputed using the MI method.
	Sensitivity 2	Change from parent-study baseline in Pain NRS at Visit 2E (Week 24)	mFAS	Prohibited medications and NSAID/acetaminophen use: treatment policy strategy; analysis will be conducted regardless of use of prohibited medications or NSAID/acetaminophen use.	Difference in the change from parent-study baseline between LOR and placebo using parent-study baseline-adjusted ANCOVA with available data.
	Sensitivity 3	Change from parent-study baseline in Pain NRS at Visit 2E (Week 24)	PPAS	1) Prohibited medications: principal stratum strategy; subjects who used prohibited medications will be excluded from this analysis. 2) NSAID/acetaminophen: treatment policy strategy; analysis will be conducted regardless of NSAID/acetaminophen use.	Difference in the change from parent-study baseline between LOR and placebo using parent-study baseline-adjusted ANCOVA.
Estimand is repeated using the OA-07-study baseline					

Secondary	Estimator	Variable	Population	Other intercurrent events	Population level summary

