	Main	Change from parent-study baseline in WOMAC Pain at Visit 2E (Week 24)	FAS	Prohibited medications and NSAID/acetaminophen use: treatment policy strategy; analysis will be conducted regardless of use of prohibited medications or NSAID/acetaminophen use.	Difference in the change from parent-study baseline between LOR and placebo using parent-study baseline-adjusted ANCOVA with available data.
	Sensitivity 1	Change from parent-study baseline in WOMAC Pain at Visit 2E (Week 24)	FAS	Prohibited medications and NSAID/acetaminophen use: treatment policy strategy; analysis will be conducted regardless of use of prohibited medications or NSAID/acetaminophen use.	Difference in the change from parent-study baseline between LOR and placebo using parent-study baseline-adjusted ANCOVA with missing data imputed using the MI method.
	Sensitivity 2	Change from parent-study baseline in WOMAC Pain at Visit 2E (Week 24)	mFAS	Prohibited medications and NSAID/acetaminophen use: treatment policy strategy; analysis will be conducted regardless of use of prohibited medications or NSAID/acetaminophen use.	Difference in the change from parent-study baseline between LOR and placebo using parent-study baseline-adjusted ANCOVA with available data.
	Sensitivity 3	Change from parent-study baseline in WOMAC Pain at Visit 2E (Week 24)	PPAS	1) Prohibited medications: principal stratum strategy; subjects who used prohibited medications will be excluded from this analysis. 2) NSAID/acetaminophen: treatment policy strategy; analysis will be conducted regardless of NSAID/acetaminophen use.	Difference in the change from parent-study baseline between LOR and placebo using parent-study baseline-adjusted ANCOVA.
Estimand is repeated using the OA-07-study baseline					

Secondary	Estimator	Variable	Population	Other intercurrent events	Population level summary
	Main	Change from parent-study baseline in WOMAC Function at Visit 2E (Week 24)	FAS	Prohibited medications and NSAID/acetaminophen use: treatment policy strategy; analysis will be conducted regardless of use of prohibited medications or NSAID/acetaminophen use.	Difference in the change from parent-study baseline between LOR and placebo using parent-study baseline-adjusted ANCOVA with available data.

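### Sensitivity 3 is said to exclude users of prohibited medication, but the per-protocol rule does not cover use affecting only Visit 2E, and excluding observed users is not a principal stratum strategy

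*SAP*

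**What the plan says.** SAP 3.2.2 makes pain NRS, WOMAC Pain and WOMAC Function at Visit 2E (Week 24) secondary endpoints, each from two baselines. SAP 9.5.2 repeats the secondary analyses in the Per-Protocol Analysis Set (PPAS).

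Appendix 2 (15.2) calls the PPAS version Sensitivity 3 and gives the same handling of prohibited medication at every visit: "Prohibited medications: principal stratum strategy; subjects who used prohibited medications will be excluded from this analysis". The main analysis and Sensitivities 1 and 2 all use a treatment policy strategy for prohibited medication.

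SAP 6.2 defines one PPAS for all visits. Subjects must have received the correct treatment, have "completed Visit 6E (Week 100") and be such that they "did not have any major protocol deviations in the current or parent study that might impact the evaluation of efficacy outcomes".

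SAP 8.2 reports what was applied: "27 subjects (29 protocol deviations) with the following types of deviations were excluded from PPAS". In its list, the OA-07 prohibited-medication category (NC04) is confined to major deviations "that would affect efficacy analysis at Visit 3E (Week 48) or Visit 6E (Week 100): n = 5". Visit 2E is not named. On grading, SAP 4.5.3 says: "These deviations were categorized as major or minor depending on the nature and timing of the interventions".

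**The concern.** Appendix 2 promises an exclusion that the rule in 8.2 does not fully deliver at Week 24. Protocol 7.6 prohibits opioids and centrally acting analgesics, both of which can change a pain score. SAP 4.5.3 says users were not automatically discontinued, so their scores remain in the data. Sensitivity 3 is the only Appendix 2 row that does anything about prohibited medication. If it agrees with the main analysis, a report could cite that as robustness to prohibited analgesics, although the Week 24 version need not have removed the relevant users.

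The strategy label is a separate matter and applies at all visits. A principal stratum is defined by what each subject would do under both treatments. The SAP defines no such stratum, no model for membership and no identifying assumption. It fits a baseline-adjusted ANCOVA to the subjects left after observed users are removed. Treatment can influence who uses prohibited medication, so the two remaining groups are selected after randomisation and may be selected differently.

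**Working it through.** **1. Is the list in 8.2 complete by its own count?** Parent study: EN01 3, NC03 2. OA-07: NC03 1, NC04 5, P01 5, P02 13. Sum: 3 + 2 + 1 + 5 + 5 + 13 = 29, which matches the stated 29 deviations. No further category could hold medication use affecting Visit 2E only.

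**2. Appendix 2 against 8.2.**

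| Use of prohibited medication in OA-07 | Appendix 2, Sensitivity 3 | 8.2 list |
|---|---|---|
| Major, affects Visit 3E or 6E | Excluded | Excluded (n = 5) |
| Major, affects Visit 2E only | Excluded | Not listed |
| Minor | Excluded | Not listed |

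**3. Can use affect Visit 2E alone?** Yes. Protocol 7.3.2 sets Visit 2E at Week 24 ± 4 and Visit 3E at Week 48 ± 4. The shortest gap within the windows is (48 − 4) − (24 + 4) = 16 weeks. The pain NRS asks about the last 24 hours (Protocol 7.1.1). Brief use around Visit 2E could alter that score and be over long before Visit 3E.

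**4. Number of analyses.** Three secondary outcomes × two baselines = 6 at Visit 2E. The same wording also governs the Visit 2E rows for mJSW, WOMAC Total and WOMAC Stiffness, which are other endpoints.

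**5. How much could retained users matter?** Shift in an arm mean = k × s / n, where k is the number of retained users, all in one arm, s is each user's score shift and n is the arm size. None of these is in the documents.
- Pain NRS, n = 250 (half of about 500, assuming equal arms), s = 1 to 3 points. One user: 0.004 to 0.012. Five: 5 × 1/250 = 0.02 to 5 × 3/250 = 0.06. Ten: 0.04 to 0.12.
- WOMAC on 0-100, n = 200, s = 15 to 30 points, five users: 5 × 15/200 = 0.375 to 5 × 30/200 = 0.75.

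**6. Does observed exclusion recover the principal stratum effect?** This was simulated with 2,000,000 subjects on assumed values: change score SD 2.5 NRS points, and use occurring when the change plus noise (SD 1) exceeds a threshold. The true effect is the same in every subject, and every observed user is excluded.

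| Users on placebo | True −0.5, estimated | True −1.0, estimated | True 0, estimated |
|---|---|---|---|
| 9.7% | −0.382 | −0.798 | −0.003 |
| 4.7% | −0.430 | −0.876 | −0.001 |
| 1.3% | −0.465 | −0.951 | −0.006 |

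Where the drug works, exclusion removes more poor responders from placebo than from LOR and shrinks the difference. With no effect the two quantities agree. Five NC04 deviations among about 500 planned subjects is 5/500 = 1%, so the last row is the closest. There the estimate keeps 0.465/0.5 = 93% and 0.951/1.0 = 95% of the true effect.

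**The case against.** The strongest reply is that no affected subject has been shown to exist. A reader might infer from the rule that subjects on prohibited analgesics were in fact kept in the Week 24 analysis. The documents do not support that. SAP 8.2 is a retrospective tally. It also says all deviations were reviewed for their effect on key efficacy endpoints, which could include Visit 2E. It refers to Appendix 1 for exclusions of subjects or of data, so exclusions at the level of a visit may be recorded there. Appendix 1 was not available for this review, and its absence is not a fault in the plan. What stands is narrower: the listed NC04 category names two visits, omits the third, and does not match Appendix 2.

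A second reply is that retaining minor users is deliberate, because 8.2 defines a minor deviation as one that does not materially reduce data quality or completeness. That is right. Use that materially distorted Week 24 pain data should have been graded major. For minor use only the Appendix 2 wording needs correcting.

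A third reply is that the label does no harm, since the SAP states the operation straight after it and makes no explicit causal claim. That limits the consequence, but the label remains wrong and costs little to replace.

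It is also tempting to relabel the analysis as hypothetical, setting users' outcomes to missing and applying the planned imputation. That would not cure the selection. SAP 7.1.4 imputes each timepoint separately from baseline and group, and the ANCOVA then uses the same two terms, so the result would essentially reproduce the exclusion analysis.

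**Conclusion.** Both parts hold in limited form. Appendix 2 and 8.2 disagree on who is excluded from the Visit 2E analyses, and observed exclusion is not a principal stratum strategy at any visit. The PPAS requirement to complete Week 100 adds another post-randomisation selection.

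The visit gap concerns major use affecting Visit 2E only, in six sensitivity analyses of secondary endpoints and the corresponding rows for other endpoints. How many subjects fall in it is unknown and may be none. On the assumed values above, a handful would move the Week 24 means little. The size of the labelling error depends on how strongly poor response drives use, which the documents do not report.

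A reader might conclude that the trial's main results are compromised. They are not. The main analyses use treatment policy in the FAS, and the Visit 2E gap does not affect the primary mJSW analysis. The label does appear in the primary endpoint's Sensitivity 3 row, where it bears only on how that row is described.

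**What to change.** 1. For the Visit 2E analyses, apply the NC04 exclusion to major use that could affect Visit 2E, through a visit-specific flag derived from the deviation and medication dates already held. State the rule in 8.2.
2. Make Appendix 2 match 8.2 on major and minor use, so that it no longer says all users are excluded if only major use is.
3. In every Sensitivity 3 row, replace the principal stratum label with per-protocol (observed exclusion) analysis. State that it compares groups selected after randomisation and is supportive only.

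There is no need to recast the analysis as hypothetical with the planned imputation, or to add a non-responder rule to the responder analyses in 9.6.3, which would be a separate strategy choice.

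The cost is SAP wording and some reprogramming, with no new data. The drawback is that PPAS numbers will differ by visit, so tables must show the count for each.

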15.3 Appendix 3 – Partial Date Imputation

Partial Date Availability	Impute Start Date		Impute End Date	
Year (YYYY)	Prior to first OA-07 injection year	YYYY-12-31	Prior to end of study year	YYYY-12-31
	Same as first OA-07 injection year	Injection Date	Same as end of study year	End of Study Date
	After first OA-07 injection year	YYYY-01-01	After end of study year	YYYY-01-01
Year and Month (YYYY-MM)	Prior to first OA-07 injection year and month	YYYY-MM-[DD, last day of month]	Prior to end of study year and month	YYYY-MM-[DD, last day of month]
	Same as first OA-07 injection year and month	Injection Date	Same as end of study year and month	End of Study Date
	After first OA-07 injection year and month	YYYY-MM-01	After end of study year and month	YYYY-MM-01
Ongoing or unknown status at end of study (e.g., no end date and unknown whether ongoing)	Not Applicable		End of Study Date	
Additional Considerations	If the end date is not missing, and the imputed start date is after the end date, the start date will be set equal to the end date.		If the imputed end date is before the start date, then the imputed end date will be set equal to the start date.	

Signature Page for VV-TMF-221629 v1.0

Reason for signing: Approved	Name: [name] Role: Associate Director, Biostatistics Date of signature: 03-Nov-2023 19:05:16 GMT+0000
Reason for signing: Approved	Name: [name] Role: Chief Medical Officer Date of signature: 03-Nov-2023 19:06:55 GMT+0000
Reason for signing: Approved	Name: [name] Role: Vice President, Biometrics Date of signature: 03-Nov-2023 19:14:51 GMT+0000

Signature Page for VV-TMF-221629 v1.0

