4.1 Changes to Overall Study Design and Plan

The sponsor elected to administratively terminate this study. All active subjects were requested to continue the study until they completed Visit 6E (Week 100); subjects injected at this visit were followed-up via phone call 10 days (+/-3 days) for safety data collection. Subjects that had already completed their Visit 6E (Week 100) were asked to schedule a termination visit as soon as possible. All procedures for the termination visit should be performed; however, as provided in the protocol, an additional X-ray was not required if a subject had an X-ray taken within the 12 weeks prior to their termination visit.

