10.1 Adverse Events

Data regarding AEs will be collected in this study. As this is an extension trial, AE collection will continue from the parent study, ongoing AEs at the end of the parent study will continue to be monitored, and new AEs that occur during this study will be recorded. Changes to ongoing AEs that occur after the parent-study EOS visit will not be recorded in the parent study. AEs will be assessed through the Termination Visit. AEs will be presented in summary tables depicting the number and percent of unique subjects experiencing each AE and the number of AEs by the following analysis periods: (1) AEs that started prior to a Second OA-07 Injection (end of the single-blind, placebo-controlled period of the study; including all AEs for subjects who only received the First OA-07 Injection to End of Study, EOS), (2) on or after Second OA-07 Injection to prior to Third OA-07 Injection (including all AEs for subjects who received the Second OA-07 Injection to EOS), and (3) on or after Third OA-07 Injection to EOS. The following summaries will be provided:

- All AEs and all SAEs by severity and relationship to study product
- AEs by highest degree of seriousness, severity, and relationship to study drug
- AEs by MedDRA system organ class and preferred term
- SAEs sorted by preferred term incidence
- AEs with incidence of greater than 2% in the active treatment group sorted by preferred term incidence
- Target-knee-related AEs and SAEs sorted by preferred term incidence
- AEs leading to study withdrawal, discontinuation of study drug, or death
- SAEs in subjects diagnosed with COVID-19

If an AE start or end date is incomplete, it will be imputed in a way that assumes maximum exposure time (see table in [Appendix 3 – Partial Date Imputation](#)). Separate subject-level listings will be provided for all AEs and all SAEs.

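### Partial AE start dates in the month or year of the second or third OA-07 injection are imputed to before that injection, so the events are counted in the wrong period

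*SAP*

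**What the plan says.** SAP 10.1 tabulates AEs in three periods. Period 1 is "1) AEs that started prior to a Second OA-07 Injection (end of the single-blind, placebo-controlled period of the study". Period 2 runs "on or after Second OA-07 Injection to prior to Third OA-07 Injection". Period 3 starts at the third injection. For an incomplete start or end date, the same section says that "it will be imputed in a way that assumes maximum exposure time" and refers to Appendix 3.

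Every start-date row of Appendix 3 is defined relative to the first OA-07 injection:

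- "Same as first OA-07 injection year" (or the same year and month): the injection date is used.
- "After first OA-07 injection year": 1 January of the known year.
- "After first OA-07 injection year and month": day 1 of the known month.

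The only further adjustment applies when a known end date exists: if "the imputed start date is after the end date, the start date will be set equal to the end date". That can move a start only earlier. No row mentions the second or third injection.

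From Visit 3E (Week 48) every subject receives LOR (SAP 4), and Protocol 10.4.4 treats Visit 3E as the first LOR exposure for placebo subjects. The first safety endpoint in SAP 3.2.3 ends at the same boundary.

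**The concern.** The table protects attribution at one boundary, the first injection, where a matching month or year yields the injection date. The AE periods are cut at two other boundaries, where a matching month or year yields a date before the injection.

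The second injection matters most. Protocol 4.2 gives additional safety information in subjects not previously treated with LOR as a reason for the crossover. An event soon after that dose is also the kind most likely to share its calendar month. If its day of onset is missing, it is listed as arising in the placebo-controlled period and drops out of the period meant to describe first exposure to LOR.

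**Working it through.** The SAP gives no figure on this point, so there is none to reproduce. The check applies the Appendix 3 start-date rule and the 10.1 periods literally.

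**Inputs.** Second injection at Week 48 (day 336) and third at Week 100 (day 700), both ± 4 weeks (Protocol 7.3.2). Assumptions: first injections fall once on each day of a 365-day span (from 15 August 2020), and true onsets are spread evenly over the stated interval after an injection. The number of partial dates is not in the documents, so results are percentages of partially dated events.

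**Example.** Injections on 15 October 2020, 16 September 2021 and 15 September 2022.

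- AE on 19 September 2021, 3 days after the second injection (true Period 2). Recorded as 2021-09 it becomes 1 September 2021; recorded as 2021 it becomes 1 January 2021. Both are Period 1.
- AE on 18 September 2022 (true Period 3). It becomes 1 September or 1 January 2022. Both are Period 2.
- If injections 1 and 2 share a calendar year (for example 20 January and 22 December 2021), a year-only start becomes 20 January 2021, which is again Period 1.

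**Month-known dates moved back.** An event moves when its onset is in the injection's month and the injection was not on day 1. For lag k days, 365 − 12(1 + k) of the 365 injection dates qualify (for the lags used here).

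- Lags 0–6: (7×365 − 12×28) / (7×365) = 2219/2555 = 86.8%.
- Lags 0–13: (14×365 − 12×105) / (14×365) = 3850/5110 = 75.3%.
- Lags 0–29: the same-month pairs number Σ n(n−1)/2 over months of n days = 7×465 + 4×435 + 378 = 5373; 5373/(365×30) = 49.1%.
- Lags 0–363 (52 weeks): 5373/(365×364) = 4.0%.

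**Year-only dates moved back.** The same count with one 365-day block, 365 − (1 + k) per lag.

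- Lags 0–6: 2527/2555 = 98.9%.
- Lags 0–13: 5005/5110 = 97.9%.
- Lags 0–29: 10485/10950 = 95.8%.
- 52 weeks: 66430/132860 = 50.0%.

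The figures are the same after the second and the third injection. Those for lags 0–29 do not change when Visit 3E is put at day 308 or day 364. The SAP rule moves 0% of true Period 1 events forward, so the error runs one way.

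**If the same-as-injection row is extended to injections 2 and 3.** For lags 0–29 after either injection, month-known misplacement falls from 49.1% to 0%. The reverse error then appears:

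- True Period 1 events in the month of the second injection but before it: 5373/(365×336) = 4.4% of month-known Period 1 events move to Period 2.
- By the same count at the third injection, 4.0% of month-known Period 2 events move to Period 3.
- For year-only dates, 66024/(365×336) = 53.8% of Period 1 events would move forward, where 66024 is the sum of min(D−1, 336) over second-injection days D = 1 to 365.

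These are upper figures, because they assume that no event is known to precede the injection.

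**The case against.** Several counter-arguments stand.

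- **Direction between arms.** A reader might infer that the rule raises the placebo AE rate and lowers the LOR rate. The documents do not support this. LOR subjects are also injected at Visit 3E, and their partially dated events move into Period 1 in the same way. The Period 1 contrast shifts only by the difference between arms, whose sign is unknown. At the third injection both periods are on LOR.
- **Reach.** With the month known, only events in the injection's own month move. The high percentages depend on onsets clustering soon after injection, which is assumed here; evenly spread onsets give 4.0%.
- **Data collection.** Onset dates are recorded and subjects are queried at each visit (Protocol 7.1.1). A phone contact at Week 52 follows Visit 3E. At study closure "subjects injected at this visit were followed-up via phone call 10 days (+/-3 days) for safety data collection". Early events are thus asked about while recall is fresh, which makes year-only dates less likely. This limits how many events are affected but does not change what the rule does to them.
- **The SAP does not say outright that imputed dates decide the period.** True, but 10.1 defines periods by start date and gives no other rule for incomplete ones.

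Two further inferences should be set aside. One is that imputing starts before the first-injection year to 31 December distorts the AE tables. Period 1 has no lower bound and no AE duration summary is planned, so no planned AE summary changes. The other is that a Period 3 of about 10 days calls for exposure-adjusted rates. Safety is descriptive, no comparison between periods is planned, and the short follow-up applies only to subjects injected at the closing Visit 6E. Annualising a short window that begins at injection could itself mislead.

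**Conclusion.** The rule gives a wrong result as written. A month-known start in the month of the second or third injection is placed before that injection unless the injection fell on day 1, and a year-only start in the injection's year is placed before it as well. The consequence that matters is at the second injection: affected events after former placebo subjects' first LOR dose are counted in the placebo-controlled period and lost from Period 2.

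Among month-known partial dates the share moved ranges from 4.0% (onsets even over 52 weeks) to 86.8% (onsets within 7 days); for year-only dates it ranges from 50.0% to 98.9%. These figures rest on the nominal visit days and on evenly spread injections and onsets. The number of partial dates is not given, so the absolute effect is unknown and may be small. No direction of bias in the comparison between arms is established.

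**What to change.** In Appendix 3, add a start-date row for AEs: when the known year and month equal those of the second or third OA-07 injection, and the event is not known to precede that injection, set the start to that injection date. An event is known to precede it if, for example, its end date is earlier or it was recorded before the injection at that visit. The existing end-date clause already returns events with a complete earlier end date to the earlier period.

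For year-only dates, keep the present rule in the main tables, because the extended row could move about 53.8% of year-only Period 1 events forward. Report how many year-only starts there are, and add a sensitivity table that assigns the ambiguous ones to the later period. Report the number of month-known partial starts too, so that a reader can judge the effect.

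SAP 12.1 uses the same table to split concomitant medications at the second injection, so state whether the new row applies there.

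The cost is one table row, two counts and one extra table, with no new data. The downside is that some true pre-injection events move to the later period: at most about 4.4% of month-known Period 1 events, if onsets are evenly spread and none is known to precede the injection, and about 4.0% of month-known Period 2 events at the third injection. At the second injection the shift is into a LOR period, which is the conservative direction for safety.
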